An important component of this proposal is the estimation of the efficacy and cost-effectiveness of interactive interventions tailored to beliefs and stage of adoption alone and together. Similar to other studies, the outcome to be compared in the cost-effectiveness analysis is the proportion of participants in each of the intervention arms who have had recommended CRC or BC screening tests during the six-month period following initial intervention. Using this design, we will be able to determine if aTIWeb, a CSC, or a TIWeb+ CSC will significantly increase adherence for CRC and/or BC screening and at what costs. If efficacy and cost effectiveness relative to other interventions are demonstrated with the TIWeb program, it could be promoted at health care visits. If the CSC increases screening at an acceptable incremental cost when added to the TIWeb, office staff could make telephone counseling calls to participants from the health care setting after the TIWeb.

B.9. Researchers have tested the effectiveness of intervening simultaneously for multiple health behaviors. In 2005, Emmons et al. reported that a telephone-delivered intervention which focused on six behavioral risk variables for colorectal cancer was effective in promoting change.⁽¹⁰²⁾ In a different research study, a home-based intervention to change smoking, high fat diet, and sun exposure produced significant changes as compared to a control.⁽¹⁰³⁾ Recently, a series of articles addressed multiple behavior research.⁽⁵⁾ Behaviors included weight management, smoking, exercise, and fruit and vegetable intake.⁽¹⁰⁴⁻¹⁰⁶⁾ All interventions that addressed multiple behavior change were effective.

[figure not shown]

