In Table 8 of the original application (see appendix), we proposed enrolling 327 for each of 8 combinations of 4 arms and 2 groups (A and B) for a study total of 2616. However, using this alternative approach will require only 1308 (327 in each of the 4 arms) women to test the primary outcome of CRC adherence. However, new studies, including our own, indicate 15-20% adherence to CRC screening in control conditions. Our initial proposal anticipated on 10% adherence in the control arm. Thus, although the new design decreases the sample size by combining the groups, a more realistic estimate of the adherence in the control group will actually increase the sample size compared to our estimate in Group A for the initial proposal. Specifically, we propose to increase our estimate of CRC adherence in all four arms, to accommodate a change in the proposed adherence in the control group from 10% to 20%. This will require 397 instead of 327 per arm (see Table 1). Thus, a sample of 397 per group at baseline (357 per group at 6 months after 10% estimated attrition) will provide 80% power to detect differences between any pair of the four randomized arms for Aim 1 (Table 1).

Revised Sample size and Power analysis for primary efficacy hypothesis of estimated CRC screening adherence rates in the combined groups of those adherent (Group A) and non-adherent (Group B) at baseline to breast cancer screening (Aim 1, primary outcome of CRC adherence)

GROUPS A and B combined

Time	Usual Care (1)	TIDVD (2)	CSC (3)	TIDVD+CSC (4)	Power
Baseline adherence	0%	0%	0%	0%	NA
Total sample size (N):	(n = 397)	(n = 397)	(n = 397)	(n = 397)	
N by baseline strata, Adherent to BC (A) Non-adherent to BC (B)	(n = 119) (n = 278)				
6 months adherence	20%	30%	40%	55%	Power for 357/arm (Groups A and B combined)
Total sample size (N):	(n = 357)	(n = 357)	(n = 357)	(n = 357)	1v2 .87 1v3 .99 1v4 .99 2v3 .80 2v4 .99 3v4 .98
N by baseline strata, Adherent to BC (A) Non-adherent to BC (B)	(n = 107) (n = 250)				

Enrollment will be stratified by women adherent to breast but not CRC screening and those adherent to neither in a 30%/70% ratio so that we will have an adequate sample to detect an 80% power for Aim 2. Aim 2 will use only the subgroup of women who are not adherent to either breast or CRC screening. This will provide at least 80% power for Group B for comparing each pair of randomized arms, when testing the secondary outcome (adherence to both CRC and BC screening) (Table 2).

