The primary cost-effectiveness measures will be the incremental cost-effectiveness ratios (ICERs) obtained by dividing the additional per target individual cost by the additional percent of target individuals who are screened by the end of the follow-up period, comparing the control group to the TIWeb group, to the CSC group, to the TIWeb+CSC group moving from the least resource-intensive to the most resource-intensive interventions (equations 1,2,3). These measures will be based on intention to treat methods and correspond to the observation period of the study.⁽¹⁴⁵⁾

Group A (cost fully allocated to BCS intervention)

- 1) $ICER_1 = (Cost_{TIWeb} - Cost_{UC}) \div (\%BCS_{TIWeb} - \%BCS_{UC})$
- 2) $ICER_2 = (Cost_{CSC} - Cost_{TIWeb}) \div (\%BCS_{CSC} - \%BCS_{TIWeb})$
- 3) $ICER_3 = (Cost_{TIWeb+CSC} - Cost_{CSC}) \div (\%BCS_{TIWeb+CSC} - \%BCS_{CSC})$

Group B (cost adjusted for joint production)

BCS: (directly allocated plus 1/2 of non directly allocated cost applied to BCS intervention)

- 1) $ICER_1 = (Cost_{TIWeb} - Cost_{UC}) \div (\%BCS_{TIWeb} - \%BCS_{UC})$
- 2) $ICER_2 = (Cost_{CSC} - Cost_{TIWeb}) \div (\%BCS_{CSC} - \%BCS_{TIWeb})$
- 3) $ICER_3 = (Cost_{TIWeb+CSC} - Cost_{CSC}) \div (\%BCS_{TIWeb+CSC} - \%BCS_{CSC})$

CRC: (directly allocated plus 1/2 of non directly allocated cost assigned to CRCS intervention)

- 1) $ICER_1 = (Cost_{TIWeb} - Cost_{UC}) \div (\%CRCS_{TIWeb} - \%CRCS_{UC})$
- 2) $ICER_2 = (Cost_{CSC} - Cost_{TIWeb}) \div (\%CRCS_{CSC} - \%CRCS_{TIWeb})$
- 3) $ICER_3 = (Cost_{TIWeb+CSC} - Cost_{CSC}) \div (\%CRCS_{TIWeb+CSC} - \%CRCS_{CSC})$

BCS & CRCS: (all costs allocated to joint BCS & CRCS intervention)

- 1) $ICER_1 = (Cost_{TIWeb} - Cost_{UC}) \div (\%BCS \& CRCS_{TIWeb} - \%BCS \& CRCS_{UC})$
- 2) $ICER_2 = (Cost_{CSC} - Cost_{TIWeb}) \div (\%BCS \& CRCS_{CSC} - \%BCS \& CRCS_{TIWeb})$
- 3) $ICER_3 = (Cost_{TIWeb+CSC} - Cost_{CSC}) \div (\%BCS \& CRCS_{TIWeb+CSC} - \%BCS \& CRCS_{CSC})$

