- **Feasibility/Clinical Relevance:** Either of the intervention strategies tested in the proposed project could easily be adapted into routine practice, if found effective. Previous studies have tailored interventions on a large number of variables necessitating lengthy interviews (Preliminary Studies). In contrast, the proposed interventions will be tailored on fewer variables and in an interactive format, thus facilitating data collection at baseline and “batch processing” the intervention. The TIWeb could even be distributed during routine care visits if a recent mammogram or CRC screening is not recorded on the chart. The addition of a CSC call from the provider’s office could also be incorporated into practice if found to have an additive value to the TIWeb.

E. Human Subjects

1. Risks to Subjects

Human Subjects Involvement and Characteristics. Participants in this study will be eligible if they have ever been a patient of any of the participating physicians; are age 50 to 75; are nonadherent to CRC or CRC and BC screening; and are able to complete telephone surveys and, depending on intervention, view a TIWeb, view a TIWeb and receive a counseling call, or receive usual care. Women will not be eligible if they have a history of adenomatous polyps, a personal history of CRC, inflammatory bowel disease or an hereditary syndrome (HNPCC\FAP). Eligibility criteria will be determined from both database records and self-report. Because this project involves mammography utilization, only women will be included.

Source of Materials: Data will be obtained from self-report at baseline and at 4-week and 6-month follow-up. Mammography status and CRC screening will be obtained from medical record data as well as self-report. Cost data will be obtained from the study administrative records.

Potential Risks: The proposed investigation does not present physical risk. Emotional or psychological risks, if they occur, would be slight. Possible fear or anxiety may be elicited when asking questions about BC,mammography, and/or colon cancer screening.

2. Adequacy of Protection against Risks

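### No planned cost-effectiveness ratio compares website plus call with website alone, although Section B.8 makes adding the call depend on that increment

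*Combined protocol and SAP*

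**What the plan says.** D.13 (Aim 2, Cost-effectiveness Analysis) obtains the primary ICERs by "comparing the control group to the TIWeb group, to the CSC group, to the TIWeb+CSC group moving from the least resource-intensive" arm to the most intensive one. Three equations follow in each of four blocks: Group A, and Group B for breast screening, for colorectal screening and for both together. The contrasts are the same in every block:

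- ICER1: TIWeb minus usual care
- ICER2: CSC minus TIWeb
- ICER3: TIWeb+CSC minus CSC

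The text after the equations adds one-way and multi-way sensitivity analysis, 1,000 bootstrap samples and 95% limits. It adds no further contrast and no rule for dominated arms.

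The uses of these results are stated elsewhere. The closing paragraph of B.8 says: "If the CSC increases screening at an acceptable incremental cost when added to the TIWeb, office staff could make telephone counseling calls" after the website. The same paragraph names a second use: "If efficacy and cost effectiveness relative to other interventions are demonstrated with the TIWeb program, it could be promoted at health care visits". Under Limitations (Feasibility/Clinical Relevance), D.13 returns to the call, which "could also be incorporated into practice if found to have an additive value to the TIWeb"; that sentence does not mention cost. Aim 2 itself, in the Specific Aims, is a general comparison of the cost-effectiveness of the four conditions.

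**The concern.** The add-the-call decision in B.8 starts from a practice that uses the website and asks what the call adds, in cost and in women screened. That is arm 4 minus arm 2 (TIWeb+CSC v TIWeb). The ladder reaches the combination from the call instead, so ICER3 is the increment for adding the website to the call. ICER2 is the increment for replacing the website with the call. Followed as written, the plan reports neither a ratio nor an interval for the increment on which B.8 makes the call's adoption depend. If the ratio is worked out only after results are known, it is a post hoc figure for a question that was stated in advance.

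**Working it through.** **1. Which arms each equation subtracts.** Number the arms 1 = usual care, 2 = TIWeb, 3 = CSC, 4 = TIWeb+CSC. ICER1 is 2 − 1, ICER2 is 3 − 2 and ICER3 is 4 − 3. The add-the-call decision needs 4 − 2. Across 4 blocks × 3 equations = 12 equations, 4 − 2 does not occur. This step needs no numerical assumption, and the point rests on it.

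**2. Planning rates for an illustration.** The D.12 power table gives 6-month colorectal adherence of 20%, 30%, 40% and 55% for arms 1 to 4, with 357 per arm. It labels arms 2 and 4 TIDVD, which I read as the TIWeb arms. The plan states no ICER to reproduce, so I checked the power figures attached to these rates. D.12 states no alpha; I assumed two-sided 0.05, pooled variance under the null and no continuity correction. For 2 v 3:

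- null SE = √(2 × 0.35 × 0.65 / 357) = 0.0357
- alternative SE = √((0.21 + 0.24) / 357) = 0.0355
- z = (0.10 − 1.96 × 0.0357) / 0.0355 = 0.85, so power is 0.80, as stated

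The other pairs also reproduce: 1v2 0.871 (stated .87), 3v4 0.981 (stated .98), and the rest above 0.99. Allowing for attrition, 357/0.9 rounds up to 397.

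**3. Illustrative ratios.** The documents give no delivery costs. Assume additive costs over usual care: w for the website, c for the call, w + c for both. Then:

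- ICER1 = w/(0.30 − 0.20) = w/0.10
- ICER2 = (c − w)/(0.40 − 0.30) = (c − w)/0.10
- ICER3 = w/(0.55 − 0.40) = w/0.15
- ICER4 (missing) = c/(0.55 − 0.30) = c/0.25

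ICER4/ICER3 = (c/0.25)/(w/0.15) = 0.6 × c/w, which equals 1 only at c/w = 5/3. Dollars per additional woman screened:

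| w, c (assumed) | c/w | ICER1 | ICER2 | ICER3 | ICER4 | ICER4/ICER3 |
|---|---|---|---|---|---|---|
| 5, 5 | 1 | 50 | 0 | 33 | 20 | 0.6 |
| 20, 30 | 1.5 | 200 | 100 | 133 | 120 | 0.9 |
| 10, 20 | 2 | 100 | 100 | 67 | 80 | 1.2 |
| 5, 20 | 4 | 50 | 150 | 33 | 80 | 2.4 |
| 5, 50 | 10 | 50 | 450 | 33 | 200 | 6.0 |

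The gap can go either way.

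**4. Whether the printed ladder can be read as it stands.** A ladder from least to most costly supports a decision only if its ratios rise. ICER1 < ICER2 needs w < c − w, so c/w > 2. ICER2 < ICER3 needs (c − w)/0.10 < w/0.15, so c/w < 5/3. Both cannot hold, so under these assumptions at least one single-component arm always drops out:

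- If the call-alone arm drops out, the path through the website survives when w/0.10 < c/0.25, that is c/w > 2.5. Its last step is then ICER4.
- The path through the call survives when c/0.20 < w/0.15, that is c/w < 4/3. Its last step is then ICER3.
- Between 4/3 and 2.5, the combination is compared directly with usual care.

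**5. Recoverability.** The ICER4 numerator is the sum of the ICER2 and ICER3 numerators, and likewise for the denominators. At w = 5, c = 20: (15 + 5)/(0.10 + 0.15) = 80, which matches the table. The two printed ratios alone do not give it; their components are needed.

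**The case against.** The strongest case against the point is that a least-to-most-costly sequence is a standard way to compare mutually exclusive options, and Aim 2 asks only for a comparison of four conditions. Calling three ratios primary does not exclude others, and the trial collects everything the fourth needs. The additive-value question is already covered on the efficacy side: the Aim 1 analysis specifies contrasts among the three intervention arms, and D.12 gives 2v4 power of .99. All of this stands, and it limits the point to a missing planned ratio and interval.

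It could also be argued that ICER4 misleads where the call-alone arm stays on the efficient path, for example at w = 20, c = 30, where ICER2 ($100) is below ICER3 ($133). The example does not show this. There ICER1 is $200, so the website alone is extendedly dominated. Once it is removed, call v usual care is 30/0.20 = $150, above $133, so the call alone drops out too. What survives is narrower: ICER4 is not the ladder's last step at every cost ratio. It should therefore be labelled for the decision it serves and accompanied by a dominance rule.

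The illustration is also open to challenge. The 20/30/40/55% rates are colorectal adherence with Groups A and B combined, while the ICER blocks are by group, several use breast or joint screening, and Group B costs are apportioned. D.8 adds questions about the website to the combination arm's call, so costs may not be additive. The illustration shows that the two ratios can differ; it does not predict by how much.

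**Conclusion.** The gap is real but limited. B.8 names the add-the-call decision and its cost criterion, and no equation in D.13 estimates TIWeb+CSC v TIWeb. That conclusion rests only on which arms are subtracted. The sizes above rest on assumed additive costs and combined-group planning rates.

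A reader might infer three stronger things that the documents do not support:

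- **That Aim 2 cannot answer its own question.** Aim 2 is worded as a general comparison, B.8 also names promoting the website, and ICER1 prices the part of that against usual care.
- **That ICER3 is an error.** It is a correct ratio for adding the website to the call, and the equations print both arms.
- **That the Limitations section repeats the cost criterion.** It repeats only the additive value.

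This is a free improvement to the cost-effectiveness aim. It does not affect the efficacy analysis, the sample size or the data to be collected.

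**What to change.** In each of the four blocks in D.13, add

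ICER4 = (Cost TIWeb+CSC − Cost TIWeb) ÷ (% screened TIWeb+CSC − % screened TIWeb),

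using that block's outcome and cost allocation. Label it as the ratio for the add-the-call decision in B.8, and take its interval from the same 1,000 bootstrap samples. For Group A, reconcile the outcome first: the printed equations use breast screening percentages, whereas Program Effectiveness makes colorectal screening the Group A outcome.

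Keep ICER1 to ICER3. Add one sentence saying that dominated and extendedly dominated arms are removed, and the ratios recomputed, before the stepwise results are read as a ladder.

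The cost is one line per block, one sentence, and one more ratio from data and bootstrap draws already planned. It should be written in before the cost and outcome data are analysed.

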For women who are nonadherent to CRC screening guidelines but adherent to BC screening (Group A), the TIWeb and the CSC will encourage CRC screening by building on the women's success with regular BC screening. For women who are nonadherent to both CRC and BC screening (**Group B**), the TIWeb and the CSC interventions will promote both CRC and BC screening simultaneously. Research indicates that individuals who undergo one type of cancer screening are more likely to pursue other forms of screening,⁽¹³⁾ making a holistic approach to cancer screening efficient and consistent with what would happen in a routine preventive care visit. In the proposed study, we also will test the cost-effectiveness of each intervention arm and the intervention interactions with demographic and practice variables. Past research^(14, 15) has shown that interventions vary in both cost and efficacy, making the addition of cost-effectiveness analysis important for future translation to practice. We will use a 2X2 factorial design with women randomly assigned to receive one of the following: 1) usual care, 2) a TIWeb, 3) a Cancer Screening Call (CSC), or 4) a TIWeb plus a CSC.

Aim 1: Compare the efficacy (adherence and stage) of four conditions to promote CRC and BC screening among women ages 50 to 75: 1) usual care; 2) a mailed TIDVD; 3) a CSC, and 4) a mailed TIDVD + a CSC. All women will be non adherent to CRC screening and may or may not be adherent to BC screening. 50 **Group A (nonadherent to CRC screening guidelines but adherent to BC screening guidelines)**

Hypothesis 1 (Primary outcome): There will be differences in CRC screening adherence and stage of adoption, when controlling for adherence to BC screening at baseline, among women who are randomized to 1) usual care; 2) a TIWeb; 3) a CSC, and 4) a TIWeb plus a CSC.

Group B (nonadherent to both CRC and BC screening guidelines)

Hypothesis 2 (Secondary outcome): In the group that is nonadherent to both CRC and BC screening at baseline, there will be differences in adherence to both CRC and BC screening and stage of adoption, among women who are randomized to 1) usual care; 2) a TIWeb; 3) a CSC, and 4) a TIWeb plus a CSC.

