Aim 2: Compare the cost-effectiveness of four conditions to promote CRC and BC screening among women ages 50 to 75: 1) usual care; 2) a TIWeb; 3) a CSC, and 4) a TIWeb + a CSC. Two groups of women will be included. **Group A** includes women who are nonadherent to CRC screening but adherent to BC screening and **Group B** includes women nonadherent to both CRC and BC screening.

Aim 3: Examine differences in intervention effects by knowledge, cancer screening beliefs, health status, demographic variables (age, race, education, and marital status), screening history, out-of-pocket costs for screening, baseline stage of adoption, health care site, and participant involvement in the intervention.

Hypothesis 1: *Interactions will be observed when intervention effects are examined by knowledge, cancer screening beliefs, health status, demographic variables (age, race, education, and marital status,), provider recommendation, screening history, out-of-pocket costs for screening, baseline stage of adoption, provider recommendation, and participant involvement in the intervention.*

Hypothesis 2: *Women receiving care at primary care practices that have on-site colonoscopy available will have greater CRC adherence than women receiving care at sites where on-site colonoscopy is not available.*

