Women for the CAB will be selected in the same way as those who participate in the larger study but will be ineligible for the larger study. Selected participants will be representative of women in the target populations with regard to age and race.⁽¹³⁰⁾ Other qualitative methodologists^(131, 132) indicate that three to five sessions are sufficient to achieve redundancy or "saturation" of information. The program's usability will be evaluated by assessing ease of use, content (leveling and appropriateness), aesthetic appeal, and cultural relevance. The program will also branch women dependent on whether answers to risk factors identify them as average or high risk for CRC due to family history. Women at average risk will be offered options of FOBT or colonoscopy. For women at increased CRC risk due to family history, colonoscopy will be recommended as the most appropriate test. If a woman at increased risk is not interested in colonoscopy, FOBT will be offered. The interactive programming allows users to receive feedback after each question or short series of questions. For individuals in **Group A (Figure 3)**, the program will provide messages to increase CRC screening that build on the success with BC screening using the common principles identified in the theoretical framework. The program will begin with risk messages that include age and stage of adherence. For women who are non-adherent to both cancer screenings (**Group B**), the program will branch to messages designed to promote both CRC and BC screening behaviors simultaneously. (**Figure 4**) For both groups of women, benefits and barriers to screening will be individually tailored. For barriers, each individual item will be listed so that all perceived barriers can be included. For women who have never had previous CRC or BC screenings or for those whose answers indicate low self-efficacy, the TIWeb will include a video of the procedures. Women receiving TIWeb will be able to observe video demonstrations of mammography and CRC screening tests as appropriate, and to listen to testimonials from health providers and survivors. Animated graphics and charts will be included. *For example, for women in Group A, message tailoring will target CRC screening because they are already adherent to BC screening. However, the message will incorporate illustrations that relate back to their adherence to BC screening.*

Table 3. Differences in Benefits Messages between Women in Group A and Group B

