Program Effectiveness: The main effect is screening compliance at 6 months from the baseline measure as determined by the randomized trial. For those in **Group A**, CRC screening is the outcome. For **Group B**, there are three outcome groups: CRC screening adherence, BC screening adherence, and adherence to CRC and BC screening. Outcomes will be determined with an “intent-to-treat” analysis by analyzing data from all women who originally consented and were randomly assigned to a research arm regardless of deviations from the protocol, the degree of treatment they received (e.g., regardless of whether TIWeb was viewed or CSC was made), or withdrawal from treatment or loss to follow-up. The use of claims data and medical records data for the main outcome of adherence will make it possible to analyze adherence at 6 months even for women who dropped out, as long as claims data for those women can be obtained.

Program Costs: To calculate the costs of the interventions, we will consider delivery costs only. Costs associated with research and development (R&D) activity or costs of screening tests are excluded. The cost of developing the TIWeb is expected to be a major pre-intervention R&D cost. Researchers have debated how to handle these “first-copy” costs and there is no universally accepted “correct” answer. First-copy costs, defined as costs incurred in establishing a regimen or intervention, are considered quasi-fixed costs independent of the number of units produced, once production is started. Generally, first-copy costs are excluded when they involve situations in which much of the intervention is already in existence and only modification is needed to adapt it for implementation. While R&D costs can be high, they are “sunk cost” from a societal perspective, in any future decision to implement the interventions. The final product developed for this study could be made available to

other organizations. We expect managed care organizations would not develop their own TIWeb, but would rely on public access or licensing arrangements to secure such educational material. However, the cost of developing the TIWeb will be calculated to inform future developers of the approximate cost of developing this type of interactive technology for health promotion interventions and to test CE analysis with and without these costs.

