Bundling screening promotion services to promote multiple screening tests for women in group B presents a special cost problem due to the difficulty of allocating cost to specific outcomes. The main difference in cost between participants in **Group A** and those in **Group B** will be participant time and telephone counseling time required to communicate information about two versus one type of screening. These costs will be directly allocated to the screening interventions by tracking time for each participant. Other implementation costs will be the same for subjects eligible for either one test or two screening tests (e.g., recruitment). For group B, we follow methods employed by Chirikos et al. (2004)⁽¹⁴³⁾ to adjust the cost estimate for subjects eligible for two screening tests. In their study of an office-based primary care tracking system to increase screening for breast, cervical, and colorectal cancer, they apportioned the cost to subjects based on the number of tests they were eligible for. If a participant was eligible for two screening tests, they were assigned ½ of the intervention cost and the full intervention cost if they were eligible for only one test. Thus, cost for participants in group B will consist of directly allocated cost for their time and nurse counselor time and other costs apportioned by the number of tests for which they are eligible (see equations below).

Cost-effectiveness Analysis: The cost-effectiveness evaluation is examined from the societal perspective and from the more limited perspective of the provider to inform future decision-makers about the relative efficiency of the alternative interventions. The analysis focuses on the incremental cost per additional individual who is adherent (i.e., has a CRC, BC, or both screening tests during the observation period) for each alternative intervention. The intervention costs will include participant time costs and resource costs and be

valued in 2010 constant U.S. dollars. This focus is consistent with the recommendations of the Report of the Expert Panel on Cost-Effectiveness in Health and Medicine.⁽¹⁴⁴⁾ The base case will be defined as the estimate of costs and effects derived from the best point estimate of intervention parameters. Planning, implementation, and participant costs will be tracked for the interventions.

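### The three Group A cost-effectiveness equations use mammography, although the plan names colorectal screening as the Group A outcome

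*Combined protocol and SAP*

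**What the plan says.** All references are to the combined protocol and SAP.

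- **Outcome.** D.13, Aim 2, Program Effectiveness states that for Group A "CRC screening is the outcome". It gives Group B three outcomes: CRC, breast, and both.
- **Population.** Aim 2 in Section A says that Group A "includes women who are nonadherent to CRC screening but adherent to BC screening".
- **Intervention.** Section A says that in Group A the website and the call "will encourage CRC screening by building on" the women's existing mammography habit. D.6.2 says that for Group A "message tailoring will target CRC screening because they are already adherent to BC screening".
- **Costs.** D.13 attributes the main cost difference between the groups to the time "required to communicate information about two versus one type of screening". For Group B it adopts a published method "to adjust the cost estimate for subjects eligible for two screening tests".
- **Equations.** D.13, Cost-effectiveness Analysis, makes the ICERs the primary measures of this analysis. The first block is headed "Group A (cost fully allocated to BCS intervention", and its three denominators are differences in %BCS. CRC screening alone is a denominator only under Group B, where the cost is "directly allocated plus 1/2 of non directly allocated cost assigned to CRCS intervention".

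**The concern.** The formulas contradict the outcome they are meant to serve. An analyst who programs the equations and one who follows Program Effectiveness would report different ratios for the same women. Under the equations, Group A's gain in CRC screening, which is what the intervention is meant to produce there, would have no cost-effectiveness result. The bootstrap confidence limits planned in the same section would carry forward whichever outcome had been programmed.

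**Working it through.** The plan reports no ICER, so there is no figure to reproduce. The check is a count, a comparison of the text, and some simple arithmetic.

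**1. Equations by group and denominator (D.13, Cost-effectiveness Analysis).**

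| Group | BCS | CRCS | BCS and CRCS | Total |
|---|---|---|---|---|
| A | 3 | 0 | 0 | 3 |
| B | 3 | 3 | 3 | 9 |
| Both | 6 | 3 | 3 | 12 |

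Group B's blocks match its three stated outcomes. Group A has one stated outcome, CRC screening, and no equation for it. Its three equations have the same form as Group B's BCS equations.

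**2. Women affected (D.12 revised sample size table).**
- At randomization: 4 × 119 = 476 of 4 × 397 = 1,588; 476/1,588 = 30.0%.
- After planned attrition: 4 × 107 = 428 of 4 × 357 = 1,428; 428/1,428 = 30.0%.

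**3. Denominators with CRCS substituted.** D.12 plans 6-month CRC adherence of 20, 30, 40 and 55% for Groups A and B combined. Assuming these rates hold in Group A:
- ICER 1: 30 − 20 = 10 points
- ICER 2: 40 − 30 = 10 points
- ICER 3: 55 − 40 = 15 points

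The documents give no planned Group A mammography rate, so the BCS denominators have no planning value.

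**4. How far the two readings could diverge (illustration only).** For the same incremental cost, the BCS-based ICER divided by the CRC-based ICER equals the CRC difference divided by the BCS difference. Take a 10-point CRC difference and assume mammography differences of:
- 5 points: 10/5 = 2 times
- 2 points: 10/2 = 5 times
- 1 point: 10/1 = 10 times
- 0.5 points: 10/0.5 = 20 times

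At zero difference the BCS ratio is undefined.

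**5. Can the Group B CRC equations stand in?** No. They carry half of the shared cost, a rule adopted for women due for two tests, and Group A women are due for one. Let C be the incremental cost and s the share of it not directly allocated. Group B's rule gives (1 − s)C + sC/2 = (1 − s/2)C. With the same CRCS denominator, a borrowed ratio would be (1 − s/2) times the fully allocated one. The documents do not give s; the factor lies between 1.0 (s = 0) and 0.5 (s = 1).

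**6. Fit of mammography as a Group A measure.** Table 6 counts breast screening action only if a mammogram follows the intervention. Take a woman whose last mammogram was under 6 months before baseline and who has no repeat by month 6. She counts as not screened, although her last mammogram is under 6 + 6 = 12 months old. Under the protocol's 15-month adherence limit, the same applies up to 15 − 6 = 9 months before baseline.

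**The case against.** The strongest reply is that this is a labelling slip that a careful analyst would correct. Program Effectiveness assigns the outcome by group, every definition of Group A in the text agrees with it, and the Group A heading already calls for full cost allocation, as suits women due for one test. CRC status and costs will be collected in any case. That stands, and it limits the seriousness of the point. It does not remove the contradiction, because the group-specific formulas are the most explicit instruction in the section. The general wording nearby, which counts a CRC test, a breast test or both, assigns no outcome to either group.

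Mammography is also not irrelevant in Group A. D.4 admits women whose last mammogram was up to 15 months ago, and D.8 promotes yearly mammography for everyone, so some will fall due during follow-up. That also stands, but it supports an additional outcome and does not replace the stated one.

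D.12 says that Aim 2 will use only women nonadherent to both screenings, which might seem to remove Group A from this analysis. There, however, Aim 2 is the label for efficacy Hypothesis 2. Section A and D.13 keep both groups in the cost analysis. The Figure 3 caption labels Group A as nonadherent to both screenings; it conflicts with the definitions and would not make mammography the sole outcome.

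Finally, steps 3 to 5 of the working do not measure an effect on any actual ICER. They rest on assumed values, and the conclusion does not depend on them.

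**Conclusion.** The concern holds. The Group A heading and 3 of 3 Group A equations specify mammography where the plan's stated outcome is CRC screening, and 0 of 12 equations supply the missing ratio. The error affects the primary cost-effectiveness measures for 476 of 1,588 planned women. Its effect on the reported ratios cannot be computed, because the documents give neither intervention costs nor Group A mammography rates. Efficacy analyses, sample size, randomization and data collection are unaffected. It should be fixed before the cost-effectiveness analysis is programmed.

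**What to change.** Replace BCS with CRCS in the Group A heading and in its three equations, so that they agree with Program Effectiveness. If mammography in Group A is of interest, keep it as a labelled additional outcome and state its 6-month definition, including how a woman who was not yet due is counted. The cost is the wording of one heading and three equations; no new data are needed.

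Optional and minor: the text orders arms from least to most resource-intensive, but the equations fix the sequence in advance. Ordering by observed cost within each perspective, and reporting dominated or extendedly dominated arms as such, would follow the stated principle. Whether that changes any ratio depends on costs the documents do not give.
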